To the best of our knowledge, there is no research on the effects of IV lignocaine infusion on intraoperative desflurane requirements in human population. Reduction of desflurane requirements when coupled with the reported benefits of IV lignocaine, will contribute to a high quality, cost effective, optimal, balanced and safe provision of anaesthesia.

OBJECTIVE

1. To investigate the effect of IV lignocaine on the end tidal desflurane concentration required to maintain BIS values between 40-60.
2. To compare intraoperative haemodynamic changes in patient with intravenous lignocaine vs normal saline.

MATERIALS AND METHODS

This prospective, double-blinded, randomised controlled study will be submitted for the approval of the Research Committee of Department of Anaesthesiology & Intensive Care, Universiti Kebangsaan Malaysia Medical Centre (UKMMC), Research & Ethics Committee, UKMMC and will be registered at ClinicalTrials.gov.

Written informed consent will be obtained from selected patients recruited into the study, which will be conducted by a single operator who is the principal investigator of this study. The study will be conducted in Hospital Universiti Kebangsaan Malaysia, Kuala Lumpur.

Inclusion Criteria:

1. American Society of Anaesthesiology (ASA) I or II patients.
2. Patients aged between 18-75 years of age.
3. Patients scheduled for elective laparoscopic cholecystectomy.
4. Patients scheduled for laparoscopic hernioplasty.
5. Patients scheduled for emergency laparoscopic appendicectomy.
6. Patients scheduled for emergency laparoscopic cystectomy.
7. Patient weight ranging from 50 – 100 kg.
8. Surgery lasting at least one hour.

Exclusion Criteria:

1. Patients with a known allergy to study drug.
2. Patients with body mass index (BMI) more than 35 kg m⁻².
3. Patients who are taking sedatives.

4. Patients with chronic substance abuse.
5. Patients with history of seizures, psychiatric disorders, cardiac failure, arrhythmias, hepatic or renal dysfunction.
6. Patients who are taking class IB antiarrhythmics or amiodarone.
7. Surgery lasting more than 3 hours.

Methodology:

Patient will be reviewed and recruited during premedication round, written consent will be explained and obtained. Patients will be fasted for at least six hours before their surgery. Tablet paracetamol 1g will be given to patients once they are called to operation theatre.

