Patients will be randomly assigned into two groups based on computer generated randomisation tables. Group A will receive intraoperative lignocaine while Group B will receive normal saline. The study drugs will be prepared by an anaesthetist registrar who is not involved in the study. Each drug syringe will be coded and given to the primary investigator who will be blinded.

In the operation theatre, intravenous access will be obtained using an 18 G cannula in all patients and infusion of crystalloid will be started. Standard monitoring will then be applied using continuous electrocardiography (ECG), non-invasive blood pressure (NIBP) monitoring, pulse oximetry and capnography. BIS (BIS Quatro™, USA) will be used to assess the depth of anaesthesia for all patients and baseline values for BIS shall be obtained prior to induction. Pre induction blood pressure (BP) and heart rate (HR) will also be recorded. The study drugs will be given 5 min before induction of anaesthesia and two syringe pumps will be used to deliver the study drugs. First, a bolus of the study drug prepared in a 10 ml syringe will be given to the patient over a period of 3 min via the syringe pump. The time of initiation of the bolus will be taken. After bolus, the BP and HR will be recorded. Subsequently, infusion of the study drug prepared in a 20 ml syringe will be started and continued until the end of surgery using the other syringe pump. The time at the start of infusion will be taken.

Group A will receive an IV bolus dose of 1.5 mg kg^{-1} of 2% lignocaine HCL diluted up to 10 ml with normal saline in a 10 ml syringe which will be delivered via a syringe pump over a period of 3 min. This is then followed by an IV infusion at the rate of $1 \text{ mg kg}^{-1} \text{ h}^{-1}$ of 2%

lignocaine HCL in a 20 ml syringe which will be administered by another syringe pump. Patients in Group B will receive an IV bolus of 10 ml of normal saline over a period of 3 min followed by an IV infusion of an equal volume of normal saline, both of which will be delivered by separate syringe pumps.

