Anaesthesia will be induced with IV fentanyl 2 mcg kg⁻¹ followed by IV propofol 2-3 mg kg⁻¹ and IV rocuronium 0.6 mg kg⁻¹. After 3 minutes of mask ventilation with only 100% oxygen, tracheal intubation using an appropriately sized endotracheal tube (ETT) will be performed to secure patient's airway. The patient will then be connected to Aisys CS² anaesthesia machine and the lungs will be ventilated with desflurane in 50% oxygen-air balance at a tidal volume of 6-8 ml kg⁻¹. End tidal CO₂ (EtCO₂) level will be maintained between 35-45 by adjusting the respiratory rate. The time of induction and intubation will be documented.

Anaesthesia shall be maintained with desflurane, in 50% oxygen-air balance with a total flow of 1.0 L min⁻¹. The end tidal desflurane (Et-Des) concentration will be adjusted to maintain a target BIS of between 40-60. BIS, MAC values, Et-Des concentration, BP and HR will be recorded every 10 min from the time of induction until the end of surgery. IV parecoxib 40 mg will be given to all patients. Boluses of IV fentanyl 50 mcg will also be given to maintain blood pressures within 20% of pre-operative levels. Dosage of fentanyl given post induction will be recorded. Bolus of IV ephedrine 6 mg will be given during hypotensive episodes with HR less than 60 beat per min while those with normal HR will be given a bolus of IV phenylephrine 100 mcg. Patients will also be given IV dexamethasone 8 mg post induction and IV granisetron 1 mg 30 mins before end of surgery to reduce the risk of post-operative nausea and vomiting. Core temperatures will be maintained above 35 °C with fluid warmer and warming blanket. If surgery lasts more than 3 hours, patient will be excluded from the study and infusion of the study drug will be stopped.

Desflurane and study infusions will be discontinued and estimation of desflurane cost will be estimated at the end of surgery. Neuromuscular block will be reversed with a combination of IV atropine 1 mg and IV neostigmine 2.5 mg. When the patient meets all criteria for extubation, the ETT will be removed. Time to extubation (defined as time from desflurane discontinuation to tracheal extubation) will be recorded. Pain score will be assessed in recovery bay and if required, patient will be given patient-controlled analgesia morphine.

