Signs of lignocaine toxicity will be monitored in all patients beginning from the time of bolus of the study drug until one-hour post operatively in the recovery bay. During general anaesthesia, signs of lignocaine toxicity that will be looked out for include an initial tachycardia and hypertension followed by prolonged PR interval, widened QRS, sinus bradycardia, ventricular arrhythmias, hypotension and cardiac arrest. When the patient is awake in recovery bay, along with late signs of lignocaine toxicity as mentioned above, patient will be observed for one hour for early signs and symptoms characterised by perioral numbness, tinnitus, light headedness, visual disturbances, muscle twitching, seizure, altered mental state and respiratory arrest. If any of these were to occur, then infusion of the study drug will be stopped and these patients will be excluded from the study and managed according to hospital protocol.

STATISCAL ANALYSIS

a) Sample size calculation:

The α value is set at 0.01 and power of study at 90%. The sample size is calculated using t- test. Calculation as derived from a study by Kuo et al (2006) and Omar et al (2019).^{6, 12}

The sample size is calculated using the “Power and Sample Size Calculations” program.

Sample size was calculated using t-test.

Requested output: Sample size

Design: Independent

Input: $\alpha = 0.01$; power = 0.9; $\delta = 0.5$; $\sigma = 0.4$; $M = 1$

[figure not shown]
Case sample size: 21 x 2 plus 10% drop out rate = 48

Sample = 24 per study group

b) Statistical test:

Analysis will be analysed using SPSS software for windows. The Kolmogorov-Smirnov test will be used to assess variable normality distribution. Categorical variables will be analysed by chi square test. Continuous variables will be compared using student's t -test. p value less than 0.05 will be regarded as statistically significant.

FLOW CHART

AAGBI Safety Guidelines

Management of Severe Local Anaesthetic Toxicity

1 Recognition	Signs of severe toxicity: 
 Sudden alteration in mental state, severe agitation or loss of consciousness, with or without tonic-clonic convulsions Cardiovascular collapse: sinus bradycardia, conduction blocks, asystole and ventricular tachyarrhythmias may occur Local anaesthetic (LA) toxicity may occur some time after an initial injection 	

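### Stopping the infusion for a suspected toxicity sign also excludes the patient from the study, so randomised and dosed patients are lost for an event the drug may cause

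*Combined protocol and SAP*

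**What the plan says.** All of this is in the combined protocol and SAP.

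- **Toxicity monitoring (Methodology, last paragraph).** Both arms are watched from the study-drug bolus "until one-hour post operatively in the recovery bay". Under anaesthesia the signs include "an initial tachycardia and hypertension followed by prolonged PR interval, widened QRS, sinus bradycardia, ventricular arrhythmias, hypotension and cardiac arrest". In recovery, early symptoms such as light headedness and tinnitus are added. The consequence is: "If any of these were to occur, then infusion of the study drug will be stopped and these patients will be excluded". The sentence goes on to say that these patients are managed under hospital protocol.
- **Infusion.** It is "started and continued until the end of surgery using the other syringe pump". At the end of surgery, "Desflurane and study infusions will be discontinued".
- **Routine haemodynamic care (Methodology, maintenance).** "Bolus of IV ephedrine 6 mg will be given during hypotensive episodes with HR less than 60 beat per min"; phenylephrine is used when heart rate is normal. "Boluses of IV fentanyl 50 mcg will also be given to maintain blood pressures within 20% of pre-operative levels". Neither instruction mentions stopping or exclusion.
- **Objective 2.** "To compare intraoperative haemodynamic changes in patient with intravenous lignocaine vs normal saline".
- **Analysis.** The statistical section names the tests and a 0.05 significance level. It defines no analysis population that would bring excluded patients back.
- **Data collection sheet.** Blood pressure, heart rate, end-tidal desflurane, MAC and BIS are recorded every 10 minutes, and total fentanyl is recorded. There is no line for a vasopressor, or for an infusion stop and its reason.

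**The concern.** The rule joins a safety action to a decision about data. The joining causes the problem, in three ways.

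First, the event comes after randomisation and may be caused by the drug. True lignocaine toxicity can occur only in the lignocaine arm, while the saline arm can contribute only false alarms. Exclusions may therefore differ between arms, and the remaining groups are no longer the groups that were randomised.

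Second, several of the intraoperative signs are blood pressure and heart rate changes, which are what objective 2 compares. Excluding a patient on such a sign is selection on that outcome. If lignocaine changes blood pressure or heart rate, the observed difference is probably pulled towards zero. If the arms do not differ, mainly numbers are lost. The same patients also leave the end-tidal desflurane comparison.

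Third, a sign first seen in recovery excludes a patient whose study treatment and intraoperative data are complete. Nothing is left to stop, and the exclusion serves no purpose for either objective.

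The data sheet could not settle the matter afterwards, because the reason for a stop would have to come from records the plan does not describe.

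**Working it through.** **1. The plan's own figure.** Inputs from the sample size section: α = 0.01, power 0.9, δ = 0.5, σ = 0.4, equal allocation. Sidedness is not stated; two-sided is taken here. With noncentrality δ / (σ√(2/n)) and 2n − 2 degrees of freedom, power is 0.885 at n = 20 and 0.904 at n = 21. So 21 per group reproduces, and 21 / 0.9 = 23.3 rounds up to 24. The 10% allowance covers 3 losses per group.

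**2. The two parts of the rule against the timeline.**

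| When the sign appears | Infusion left to stop? | Intraoperative data | Effect of exclusion |
|---|---|---|---|
| During surgery | Yes | Recorded up to the stop, and can continue | Removes a randomised patient, partly on objective 2's outcome |
| In recovery, up to one hour | No | Complete | Removes a patient with full data |

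In neither row does protecting the patient require discarding the data.

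**3. Illustration of selection on the outcome.** The documents give no event rate and no cut-off, so every input here is assumed. Let the analysed blood pressure value be N(0,1) in one arm and N(−0.5,1) in the other, and remove values below c. With a = c − μ, the retained mean is μ + λ and the retained variance is 1 + aλ − λ², where λ = φ(a) / (1 − Φ(a)). The standardised difference divides by the root mean of the two retained variances.

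| c | Removed, higher / lower arm | Raw difference | Retained SDs | Standardised difference |
|---|---|---|---|---|
| −2 | 2.3% / 6.7% | 0.416 | 0.942, 0.879 | 0.457 (9% smaller) |
| −1.5 | 6.7% / 15.9% | 0.351 | 0.879, 0.794 | 0.419 (16% smaller) |
| −1 | 15.9% / 30.9% | 0.278 | 0.794, 0.697 | 0.373 (25% smaller) |

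When the trigger is any of nine readings and the patient mean is analysed (assumed within-patient correlation 0.3 to 0.7), simulation gives 0.46–0.48, 0.43–0.46 and 0.38–0.42 at the same three removal rates in the higher arm. The model ignores the correction of blood pressure by fentanyl and vasopressors. The lower rows need exclusion rates that only an unlikely reading of the rule would produce. The table shows direction and is not an estimate.

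**4. What keeping the patients costs objective 1.** Suppose a fraction f of the lignocaine arm stops and loses a share s of the effect (both assumed). The difference becomes 0.5(1 − fs). The lignocaine-arm variance becomes 0.16 + 0.25s²f(1 − f), averaged with 0.16 for the saline arm. With 24 per arm, two-sided:

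| f | s | Difference | Power at 0.05 | Power at 0.01 |
|---|---|---|---|---|
| 0 | – | 0.500 | 98.9% | 94.5% |
| 0.05 | 0.5 | 0.4875 | 98.4% | 93.0% |
| 0.10 | 0.5 | 0.475 | 97.9% | 91.2% |
| 0.05 | 1 | 0.475 | 97.7% | 90.6% |
| 0.10 | 1 | 0.450 | 95.8% | 85.4% |
| 0.20 | 1 | 0.400 | 89.2% | 71.6% |

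Both levels are shown because the plan sizes at 0.01 and tests at 0.05. Losing all effect is a harsh assumption, since readings before the stop are unaffected.

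**The case against.** A reader might infer more: that any tachycardia, bradycardia, hypertension or hypotension stops the infusion and excludes the patient, so that routine pressure dips empty the trial and objective 2 is heavily distorted. The sentence does say any, and it gives no threshold or attribution step. The documents nevertheless make this the less plausible reading. The signs are introduced as signs of lignocaine toxicity, and the intraoperative list describes a sequence. The sentence ends with management under hospital protocol, which fits a toxicity event. The plan reproduces a guideline on severe local anaesthetic toxicity with a recognition section. Hypotension has its own routine treatment, and a 10% dropout allowance does not fit a plan to exclude every hypotensive patient.

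The other side can also say that exclusions should be few. The Introduction reports plasma levels below 5 mcg/ml at 1–2 mg/kg/h and describes cardiovascular toxicity as uncommon, usually above 10 mcg/ml. This trial infuses 1 mg/kg/h, the bottom of that range, after a 1.5 mg/kg bolus. Finally, a broad stopping rule is defensible under anaesthesia, when patients cannot report symptoms and plasma levels are not widely available.

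All of this stands, and it limits the size of the problem. It does not justify exclusion, because the patients who are stopped, however few, still leave the analysis for a reason linked to treatment. Blinding limits biased judgement but does not prevent selection if the drug itself causes the sign. One caveat remains: the flow chart's content is missing from the available text, so it cannot be ruled out that it addresses exclusions.

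**Conclusion.** The point holds in a limited form. As written, the rule excludes randomised, dosed patients for post-randomisation signs that the drug may cause. Some of those signs are components of objective 2's outcome, and some can appear only after the intraoperative data are complete. This is a stated rule that can bias the comparison, and no analysis population corrects it.

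The size is unknown and probably small at this dose, if staff act only on suspected toxicity. The attenuation of 9% to 25% in the table belongs to the literal reading with assumed cut-offs and a 0.5 SD difference, and should not be quoted as expected bias. Nor is a loss of power for objective 1 claimed: with 21 patients left per arm, power is 97.7% at 0.05 and 90.4% at 0.01. The change is worth making because it is cheap and leaves patient protection as it is.

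**What to change.** 1. Leave the safety stopping rule unchanged. Replace exclusion from the study with wording such as: *study drug discontinued; all recorded data kept and analysed in the randomised group*. State that this includes patients whose sign is first seen in recovery, and that intraoperative recording continues after a stop.
2. Add data-sheet lines for infusion stop (time and reason) and for vasopressor given.
3. Tabulate infusion stops by arm, with reasons.

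The cost is a short wording change and two data-sheet lines, with no extra patients or procedures. Shortened infusions will slightly dilute the end-tidal desflurane effect. In the assumed full-loss case with 5% to 10% of the lignocaine arm stopped, power at the 0.05 test level stays above 95%; at 0.01 it falls below the planned 90% when 10% are stopped.

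Whether routine blood pressure and heart rate events, already treated under the maintenance instructions, should be carved out of the stopping rule is a clinical clarification for the investigators. It would help consistency, but it trades against a narrow therapeutic index and is not part of the required change.

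### Randomised, dosed patients are excluded for a toxicity sign or for surgery over 3 h, and no visible text keeps their data, even when the sign first appears after the intraoperative record is complete

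*Combined protocol and SAP*

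**What the plan says.** All of this is in the combined protocol and SAP.

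- **Order of events (Methodology).** Patients are randomised, and the study drug is started 5 min before induction.
- **Toxicity rule (Methodology, toxicity monitoring).** Monitoring runs from the bolus to one hour after surgery. Under anaesthesia the signs are "an initial tachycardia and hypertension followed by prolonged PR interval, widened QRS, sinus bradycardia, ventricular arrhythmias, hypotension and cardiac arrest". In the recovery bay, "patient will be observed for one hour for early signs and symptoms characterised by perioral numbness", with further neurological signs listed after that. Directly after both lists comes the rule: if any of them occurs, "then infusion of the study drug will be stopped and these patients will be excluded from the study".
- **Duration rule.** Exclusion criterion 7 reads "Surgery lasting more than 3 hours". The Methodology repeats it as an action during the case: "If surgery lasts more than 3 hours, patient will be excluded from the study", and the infusion is stopped.
- **Recording window (Methodology).** "BP and HR will be recorded every 10 min from the time of induction until the end of surgery"; the same sentence covers end-tidal desflurane (Et-Des), MAC and BIS. At the end of surgery, "Desflurane and study infusions will be discontinued".
- **Analysis (Statistical analysis, b).** The section names the normality check, the chi-square test, the t-test and a 0.05 threshold. It gives no analysis set and no rule for excluded patients. The flow chart is not visible in the text available for review.
- **Data collection sheet.** There is no field for suspected toxicity, an early infusion stop or a reason for exclusion.

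**The concern.** A safety action (stop the infusion) is joined to a data action (remove the patient). The first protects the patient; the second does not. Removing patients because of something that happens after dosing gives up the protection of randomisation whenever that event can depend on the drug, and the Introduction itself attributes these signs to lignocaine.

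Two things are at stake. One is loss of valid records, most plainly where the sign is first seen in recovery. The other is selection. If more patients are removed from one arm, and those removed differ in Et-Des, blood pressure or heart rate, the comparison of the remaining patients is biased. This can happen even with no true haemodynamic difference: it is enough that exclusions for ECG or neurological signs are more frequent in one arm and correlate with blood pressure. Without a field for exclusions on the data sheet, a reader of the results could not judge how far this had happened.

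**Working it through.** **1. The plan's own sample size.** Inputs from Statistical analysis, a): α = 0.01, power 0.9, δ = 0.5, σ = 0.4, ratio 1:1. A two-sample t-test (noncentral t, two-sided) gives power 88.5% at 20 per arm and 90.4% at 21, so 21 per arm reproduces. For drop-out, 21 / 0.9 = 23.3, rounded up to 24 per arm, 48 in total. The allowance is 48 − 42 = 6 patients.

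**2. Is power the problem?** With all 48 analysed, power is 94.5%. If the lignocaine arm alone loses two patients (22 v 24) it is 93.3%; if it loses six (18 v 24) it is 89.7%. A few exclusions are affordable, so the issue is selection and lost data.

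**3. Signs first seen in recovery.** Set the windows side by side:

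| Item | Ends |
|---|---|
| Et-Des, MAC, BIS, BP, HR readings | end of surgery |
| Study infusion | end of surgery |
| Toxicity signs that trigger exclusion | one hour after surgery |

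A patient who first reports tinnitus in recovery has a complete record under full allocated exposure, and there is no infusion left to stop. Exclusion changes only the dataset. This step needs no assumed rate.

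**4. Possible shift in Et-Des.** The documents give no exclusion rate and no link between signs and Et-Des, so both are assumed. Suppose a fraction p of the lignocaine arm is removed, being those highest on a normally distributed tendency to show signs that has correlation r with Et-Des, and no controls are removed. The mean of those retained then shifts by

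r × σ × φ(z) / (1 − p), where z is the upper-p normal quantile and σ = 0.4.

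- One of 24: p = 0.0417, z = 1.732, φ(z) = 0.0891, ratio 0.0891 / 0.9583 = 0.0929. Shift 0.007 at r = 0.2 and 0.019 at r = 0.5.
- Two of 24: p = 0.0833, z = 1.383, φ(z) = 0.1533, ratio 0.1533 / 0.9167 = 0.1673. Shift 0.013 at r = 0.2 and 0.033 at r = 0.5.
- Harsher case, p = 0.20 and r = 0.5: ratio 0.350, shift 0.07, so 0.5 becomes 0.43 or 0.57.

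The sign of r is unknown. The Introduction ties cardiovascular depression to higher volatile doses, so excluded patients could have Et-Des above or below the rest.

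**5. Surgery over 3 h.** Duration is known only after dosing, but nothing in the documents suggests that it differs by arm. The expected result is lost records.

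**6. Cost of keeping everyone.** If a fraction f of lignocaine patients stop early and lose a share L of the effect, the difference becomes 0.5 × (1 − f × L). For f = 0.05 and L = 0.5 this is 0.4875; for f = 0.10 and L = 1 it is 0.45 (f and L assumed).

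**The case against.** **The wording may mean withdrawal from treatment only.** The toxicity sentence is a safety instruction, the statistical section never says that readings are dropped, and the missing flow chart might show who is analysed. This cannot be ruled out. But both rules state the exclusion separately from the infusion stop, and no visible text keeps the data. If treatment withdrawal is all that is meant, the fix simply says so.

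**The stronger haemodynamic reading.** A reader might infer that any episode of tachycardia, hypertension, bradycardia or hypotension removes a patient, so that objective 2 is cut off on its own outcome. The documents do not support this. The signs are given as a sequence characteristic of toxicity. The Methodology treats raised pressure with fentanyl, and hypotension with ephedrine or phenylephrine, without exclusion. The Introduction describes cardiovascular toxicity as uncommon and late. Routine treated events are probably meant to stay in. What remains is that no threshold separates them from suspected toxicity.

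**Toxicity should be infrequent and judgement is blinded.** The Introduction places infusions of 1–2 mg/kg/h below the plasma level at which neurological signs begin, and this trial infuses 1 mg/kg/h after a 1.5 mg/kg bolus. The investigator is blinded and all patients are monitored alike. Both points stand, and they are why the likely effect is small. Blinding limits deliberate selection, but not selection produced by a drug effect.

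**The one-hour minimum.** A reader might infer that "Surgery lasting at least one hour" also removes dosed patients. It is an eligibility line only; no text excludes a dosed patient for short surgery.

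**Conclusion.** The point holds and should be fixed, at modest weight. Followed as written, the rules remove randomised, dosed patients for a possible drug effect or for long surgery, and nothing visible keeps their data. The firmest part is the recovery-bay case, which rests on the text alone. The size and direction of any selection bias cannot be computed from the documents, which give no sign rate, threshold or blood-pressure variability. For Et-Des it is probably small: about 0.01 to 0.03 against 0.5 with one or two of 24 excluded, under the assumed correlation of 0.2 to 0.5 and exclusions in the lignocaine arm only. The 3 h rule mainly costs data.

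A reader might infer that the primary result or the power is seriously threatened; the figures do not support that. No size is offered for objective 2, because every input would have to be invented.

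**What to change.** Keep both infusion stops. In the two Methodology sentences, replace the exclusion wording with:

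> All randomised patients who receive study drug are analysed in their allocated group, using all Et-Des, BP and HR readings taken until desflurane is discontinued, including those after an early infusion stop. Signs first seen in recovery do not remove intraoperative data. Suspected toxicity and early stops are recorded on the data sheet and reported by group.

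Apply the 3 h criterion as expected duration at enrolment. Add two data-sheet fields: suspected toxicity (sign and time) and early stop (time and reason). A per-protocol set may serve as a sensitivity analysis.

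The cost is wording and two fields, with no extra patients or procedures. The downside is slight dilution from patients with shortened exposure: 0.5 becomes about 0.49 to 0.45 if 5–10% of lignocaine patients stop early and lose half to all of the effect (assumed). A patient stopped before any Et-Des reading can only be counted by arm.

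### The sample size uses α = 0.01 with 90% power, but the only decision rule is p < 0.05, so the stated α and power are not those of the planned test

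*Combined protocol and SAP*

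**What the plan says.** Both statements are in the statistical analysis section of the combined protocol and SAP.

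- **a) Sample size calculation.** "The α value is set at 0.01 and power of study at 90" per cent. The program input line repeats α = 0.01 and power 0.9, with δ = 0.5, σ = 0.4 and M = 1 (equal groups). The method is a t-test with "Design: Independent". The result is "Case sample size: 21 x 2 plus 10% drop out rate = 48", then "Sample = 24 per study group".
- **b) Statistical test.** "Continuous variables will be compared using student's t -test", and "p value less than 0.05 will be regarded as statistically significant". No variable is exempted.

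The documents do not say whether tests are one-sided or two-sided, and they do not name the variable that the sample size refers to. The first objective is the likely candidate: "To investigate the effect of IV lignocaine on the end tidal desflurane concentration required to maintain BIS values between 40-60".

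**The concern.** A sample size calculation describes the properties of a particular test: its false-positive rate and its chance of detecting a given difference. Here the calculation describes a test at 0.01 and the analysis prescribes one at 0.05. No part of the plan applies 0.01 to an analysis, and none explains the gap, for instance as a multiplicity adjustment or a deliberate planning margin.

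What is at stake is how a result with p between 0.01 and 0.05 is read. It is significant under subsection b) but does not meet the α in subsection a). It could be reported as a positive finding from a trial designed at 1%, when it meets only a 5% rule.

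**Working it through.** **Inputs** (all from subsection a) unless noted): δ = 0.5, σ = 0.4, equal groups, independent t-test, α = 0.01, power 90%, 10% dropout. The analysis threshold of 0.05 is from subsection b). Sidedness is not stated and is inferred in step 1.

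**Formulas.** The standard error of the difference is SE = σ × √(2/n), with df = 2n − 2. Two-sided power is the probability that a noncentral t variable, with noncentrality δ/SE, falls beyond ± t(1 − α/2, df).

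**1. Reproduce the planned size.** The standardised difference is 0.5/0.4 = 1.25. The smallest n per group with power of at least 90% is:

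| α | Sides | n per group | Power at that n |
|---|---|---|---|
| 0.01 | two | **21** | 90.4% (n = 20 gives 88.5%) |
| 0.01 | one | 19 | 91.6% |
| 0.05 | two | 15 | 91.1% (n = 14 gives 88.9%) |
| 0.05 | one | 12 | 90.7% |

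Only two-sided 0.01 gives the plan's 21. The figure is therefore correct for its inputs, and 0.01 is not a typing slip for 0.05. Dropout: 21 × 1.1 = 23.1, rounded up to 24 per group, 48 in total, as stated.

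**2. Power under the rule in subsection b).** At n = 21, SE = 0.4 × √(2/21) = 0.1234 and noncentrality = 0.5/0.1234 = 4.05.

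| n per group | Power at two-sided 0.01 | Power at two-sided 0.05 |
|---|---|---|
| 21 | 90.4% | 97.7% |
| 24 | 94.5% | 98.9% |

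The mismatch does not depend on the inferred sidedness: one-sided 0.05 gives 99.0% at n = 21.

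**3. Observed differences on which the two levels disagree.** The critical difference is t × SE, taking the observed SD as 0.4.

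- n = 21, df = 40: 2.021 × 0.1234 = 0.249 at α = 0.05; 2.704 × 0.1234 = 0.334 at α = 0.01.
- n = 24, df = 46: 2.013 × 0.1155 = 0.232 at α = 0.05; 2.687 × 0.1155 = 0.310 at α = 0.01.

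Observed differences of about 0.25 to 0.33 (n = 21) or 0.23 to 0.31 (n = 24) are significant at 0.05 but not at 0.01.

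**4. How often that happens.** P(0.01 ≤ p < 0.05) = power at 0.05 − power at 0.01. With no effect it is 5% − 1% = 4.0%. At the planned 0.5 it is 97.7% − 90.4% = 7.3% (n = 21) or 98.9% − 94.5% = 4.4% (n = 24). Other true differences are not in the plan and are assumed here to show the range:

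| True difference | n = 21 | n = 24 |
|---|---|---|
| 0 (no effect) | 4.0% | 4.0% |
| 0.1 | 8.8% | 9.4% |
| 0.2 | 19.9% | 21.3% |
| 0.3 | 25.7% | 24.9% |
| 0.4 | 18.3% | 14.7% |
| 0.5 (planned) | 7.3% | 4.4% |
| 0.6 | 1.6% | 0.7% |

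The maximum is about 26%, at a true difference near 0.3. Simulation of 200,000 trials agreed to within 0.1 percentage point at 0, 0.3 and 0.5.

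**The case against.** The best defence is that sizing at a stricter level than the test uses is conservative. A sample with 90% power at 0.01 has at least 90% at 0.05, so the power statement survives as a minimum. Subsection b) gives the analyst one unambiguous instruction, a 5% threshold is not itself a defect, and nothing in the plan says that results will be reported against 1%. At the two true differences that the design defines, the disputed range has a probability of only 4.0% to 7.3%. The 26% figure needs a true difference that the plan never mentions.

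Most of this stands as a limit on the size of the problem. The error favours power, the consequence is small, and the 26% should not drive the severity. It does not remove the inconsistency. The plan says that α is set at 0.01, not that 0.01 is a margin around a 5% test, and the false-positive rate that it declares is one fifth of the one that it prescribes. If a margin was intended, one sentence saying so, with the power restated, would settle the matter.

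A further objection is that a rule at 0.01 for the sized comparison means little while that comparison is undefined. That is fair, and the fix takes it into account.

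**Conclusion.** The concern holds and should be fixed. The sample size is correct for its inputs, but its α is not the level at which the test will be judged. Under the written rule the per-test type I error is 5% against a stated 1%, and power is 97.7% at 21 per group (98.9% at 24) against a stated 90%. The trial is not underpowered at either level, and the t-test is not invalidated.

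The power figures are conditional on the plan's δ of 0.5 and σ of 0.4 and on two-sided testing, which is inferred from the match to 21 per group. The documents do not show which level was intended.

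**What to change.** Before unblinding, state one two-sided α for the comparison that the trial was sized on and use it in both subsections. The sponsor must say which level was meant.

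- **Option (i): keep 0.01.** Add to subsection b) that the comparison used for the sample size is judged at two-sided p < 0.01, and keep 24 per group. The sentence must name the variable, inferred to be end-tidal desflurane from objective 1. It must also name the summary tested, because end-tidal desflurane is recorded every 10 minutes. The cost is a stricter threshold: at 21 per group, the difference detectable with 90% power is 0.50 rather than 0.41.
- **Option (ii): keep 0.05.** In subsection a), change the α and power sentence and the program input line to two-sided 0.05, and restate the power as about 97.7% for 21 evaluable per group. The stated type I error then rises from 1% to 5%. The sample also exceeds what 90% power at 0.05 needs: 15 × 1.1 = 16.5, so 17 per group or 34 in total, against 48 planned, a difference of 14 patients. The text should say openly that the power is restated for a sample already chosen.

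Either option is a short text change and needs no extra patients.
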